## **INTRODUCTION:**

Acne keloidalis nuchae (AKN) is one of the chronic forms of scarring folliculitis, affecting predominantly the occipital scalp, seen mostly in men of African descent. It has been reported in a few Caucasians and other ethnic groups. The reported prevalence in African Americans ranges from 0.5% to 13.6%. The pathogenesis is yet to be elucidated. However, inflammation is central to its pathogenesis. Standard dermatologic recommendations for early or mild disease with non keloidal lesions include potent topical steroids which may be combined with topical retinoids. Early to mild disease, for the purpose of this study, includes class I and Class II AKN as defined by Lullo et al.

Combining a topical corticosteroid with a topical retinoid allows for dual mechanistic action in the management of AKN; the topical corticosteroid, provides a primarily anti-inflammatory effect and the vitamin A derivative, impairs keratinocyte proliferation. Duobrii has the advantage of being the only high potency topical steroid-retinoid combination approved by the FDA with dermatologic indication. We are, thus, proposing, the off-labeled use, of Duobrii for the management of early-mild AKN.

## **HYPOTHESIS:**

### **Primary Hypothesis:**

1. Subjects treated with Duobrii will experience significant clinical improvement in lesion counts, symptoms associated with AKN as well as minimal dyspigmentation when compared to patients receiving placebo.

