## **ENDPOINTS:**

### **Primary Endpoint**

- The primary endpoint will be clinical improvement as assessed by lesion counts and captured by photography.

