### **Secondary Endpoint**

- Patient reported outcome, improvement in severity of AKN associated symptoms as well as degree of dyspigmentation.

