## **DATA ANALYSIS:**

### **Sample Size Considerations**

A sample size of n=20 Duobrii-treated subjects allows 80% power at 5% significance to detect a minimum reduction of 35% in the median number of lesions at week 12 with the one-sided Wilcoxon nonparametric test. This calculation assumes an average count of 15 AKN lesions at baseline and a standard deviation of 7 lesions around the mean difference at week 12, and a drop-out rate of 30%. These numbers are based on data reported by Okoye et al. (2014), who compared lesion counts at week 16 to baseline in a set of 11 UVB-treated subjects. The sample size calculation is based on the asymptotic relative efficiency of the Wilcoxon test compared to paired Student's t-test. A sample size of n=20 treated subjects compared to n=10 placebo-treated ones allows 80% power at 5% significance to detect a minimum 50% difference between proportions of patients with a reduced number of AKN lesions. This calculation is based on the application of a one-sided Z-test for the difference between two independent proportions and also assumes a maximum 30% dropout rate within each arm.

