## **Primary Endpoint**

The primary analysis for the primary endpoint will test for a reduction in lesion counts after 12 weeks of treatment. We will apply the two-sided Wilcoxon test to assess the significance of the difference between pre- and post-treatment median numbers of lesion counts. The secondary analysis will compare the reduction in lesion counts between active and placebo groups after 12 weeks. For this purpose, we will apply the Z-test to verify the hypothesis that the proportions of patients with reduced AKN lesions differ between active and placebo groups. A more comprehensive analysis will adjust a generalized linear mixed-effects model, based on Poisson distribution, including time and treatment group as fixed factors and a random intercept for each subject. This model will include the whole time-course and contrasts of interests will be estimated.

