## **Secondary Endpoints**

We will compare the improvement in the severity of AKN symptoms, degree of dyspigmentation, and patient-reported outcomes (DLQI and NRS) between time points (Baseline, 4, 8, and 12 Weeks) and groups (placebo and active) with the nonparametric tests described for the primary endpoint. We will also adjust, for each outcome, a generalized linear mixed-effects model including time, treatment group, their interaction as fixed effects, and a random intercept for each participant. This modeling strategy will decide each outcome's probabilistic distribution and link function based on goodness-of-fit criteria. The Spearman correlation coefficient will measure the association between reduction in lesion counts and improvement in patient-reported outcomes. In addition, we will compare the percent area of the treatment area affected with dyspigmentation (hypo- or hyperpigmentation) at each visit.

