### The Numeric Pain Rating Scale Instructions

Please indicate the intensity of current, best, and worst pain levels over the past 7 days on a scale of 0 (no pain) to 10 (worst pain imaginable).

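### The primary hypothesis covers lesion counts, symptoms and dyspigmentation, but only lesion counts are a primary endpoint, and the other outcomes are compared across visits and arms with no key score, key visit, testing order or multiplicity control

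*Combined protocol and SAP*

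**What the plan says.** **Hypothesis.** The only primary hypothesis is that treated subjects will have "significant clinical improvement in lesion counts, symptoms associated with AKN as well as minimal dyspigmentation when compared to patients receiving placebo". It is a comparison with placebo and names three domains.

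**Endpoints.** The primary endpoint has one domain: "The primary endpoint will be clinical improvement as assessed by lesion counts and captured by photography". The other two domains are secondary: "Patient reported outcome, improvement in severity of AKN associated symptoms as well as degree of dyspigmentation".

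**Data Analysis, Sample Size Considerations.** Both power statements concern lesions. The first says that a treated group of 20 "allows 80% power at 5% significance to detect a minimum reduction of 35% in the median number of lesions at week 12". That calculation is one-sided. The second concerns the proportions of patients in each arm whose lesion count falls. Nothing is sized on symptoms or dyspigmentation.

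**Data Analysis, Primary Endpoint.** The primary test is pre/post: "We will apply the two-sided Wilcoxon test to assess the significance of the difference between pre- and post-treatment median numbers of lesion counts". The between-arm comparison, a Z-test of proportions, is called the secondary analysis.

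**Data Analysis, Secondary Endpoints.** Symptom severity, dyspigmentation, DLQI and NRS are compared "between time points (Baseline, 4, 8, and 12 Weeks) and groups (placebo and active", using the nonparametric tests of the primary endpoint and then a mixed model for each outcome. Dyspigmentation area is also compared at each visit.

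**Appendix D.** The pain NRS alone asks for three ratings: "Please indicate the intensity of current, best, and worst pain levels over the past 7 days". The itch NRS has the same three.

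**The concern.** The hypothesis and the endpoints do not match, and nothing in the plan connects them. It does not say whether all three domains must succeed, or how the hypothesis would be judged if lesions improved and symptoms did not.

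The symptom domain also has no defined test. Several overlapping scores are compared at several visits, and none is named as the one that counts. Because symptoms sit inside a primary hypothesis that uses the word significant, a single low p-value among many could be reported as support for that part of it. With 30 participants and an allowance of 30% dropout, such a result would be hard to tell from noise.

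**Working it through.** **1. The plan's own figure.** The reduction to detect is 0.35 × 15 = 5.25 lesions, with SD 7. At one-sided 5% and 80% power, the normal formula gives (1.645 + 0.842)² × (7/5.25)² = 10.99, and the paired t-test needs 13. Dividing by the Wilcoxon efficiency 3/π = 0.955 (normality assumed) gives 13.6, so 14. Allowing for 30% dropout, 14/0.70 = 20. The stated n = 20 is reproduced, for a pre/post lesion-count test only. The same dropout leaves 20 × 0.7 = 14 and 10 × 0.7 = 7 completers.

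**2. The three domains side by side.**

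| Domain | In primary hypothesis | Endpoint status | Sized | Key score, visit or order |
|---|---|---|---|---|
| Lesion counts | yes | primary | yes | week 12 |
| Symptoms | yes | secondary | no | none |
| Dyspigmentation | yes | secondary | no | none |

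**3. Counting scores, if each item is analysed separately (an assumption).**
- NRS pain: 3 (Appendix D)
- NRS itch: 3 (Appendix D)
- Symptom survey: at least 3; Study Design Overview names pain, pruritus and burning and leaves the list open
- Symptom scores: 3 + 3 + 3 = 9
- Adding DLQI and dyspigmentation area: 11

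Over weeks 4, 8 and 12 this is 9 × 3 = 27 symptom comparisons between arms, or 11 × 3 = 33 in all.

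**4. Chance of a false result in favour of Duobrii.** A two-sided 5% test gives a false result in one given direction 2.5% of the time. For k independent tests the chance of at least one is 1 − 0.975^k:
- k = 1: 2.5%
- k = 9 (symptom scores, week 12 only): 20.4%
- k = 27 (symptom scores, three visits): 49.5%
- k = 33 (all scores, three visits): 56.6%

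The scores are not independent, since they are overlapping ratings repeated in the same patients. The documents give no correlations, so a range was assumed: 0.3–0.7 between scores and 0.6–0.7 between visits. Simulated null trials with rank-sum tests, 14 versus 7, give:
- nine symptom scores, three visits: about 22–33%
- nine symptom scores, week 12 only: about 10–17%

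A multivariate-normal approximation for nine scores and three visits, with visit correlation 0.7, gives 31.5%, 25.9% and 19.9% at score correlations of 0.3, 0.5 and 0.7. The two methods agree to within a few points. Relative to one pre-specified score, 22/2.5 = 8.8 and 33/2.5 = 13.2, so the inflation is roughly 9- to 13-fold.

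**5. Sensitivity.**
- If only the four named outcomes (symptoms, dyspigmentation, DLQI, NRS) are analysed, one score each, there are 4 × 3 = 12 tests. The chance is then about 15–18% with correlation, and 1 − 0.975^12 = 26.2% if independent.
- Counting false results in either direction over all 33 tests gives 1 − 0.95^33 = 81.6% if independent and about 51–69% with score/visit correlations from 0.3/0.6 to 0.6/0.7. That includes results favouring placebo, so it is not the chance of a false benefit.
- Pre/post tests and the repeated mixed-model analyses are not counted. Pre/post tests can also be positive through placebo response or natural change.

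**The case against.** **These are secondary outcomes in a small single-centre trial, and the lesion-count result is unaffected.** The second part is correct and limits the seriousness. The first would answer the point if the Hypothesis section did not place symptoms and dyspigmentation inside the primary hypothesis. The plan does not call these analyses exploratory.

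**The inputs are inferred.** This stands. The 5% level appears only under Sample Size Considerations. Nothing says that current, best and worst NRS ratings, or the symptom items, are analysed separately, and the symptom survey's scoring is not visible. No between-arm rank-sum test is named: the section that Secondary Endpoints refers back to gives a pre/post Wilcoxon test and a Z-test of proportions. The two-sided reading follows the primary test, although the sample size is one-sided; one-sided 5% tests would raise the false-benefit rates. The figures are illustrative, and 27 or 33 tests is close to the largest reading.

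**A reader might infer that a false symptom benefit is more likely than not.** The documents do not support this. Figures above 50% mostly count errors in either direction or include outcomes other than symptoms. In the benefit direction, passing 50% needs ln 0.5 / ln 0.975 = 27.4, so 28 independent tests. The nine symptom scores give 27, and they are correlated.

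**A reader might also infer that any one significant score confirms the primary hypothesis.** The plan contains no such rule. The hypothesis joins its domains, and read that way one stray symptom p-value would not confirm it. The weakness is that no rule is stated.

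**Conclusion.** The point holds. The primary hypothesis covers three domains versus placebo, one of them is the primary endpoint, and the others are compared repeatedly without a key score, key visit, order or multiplicity control. This follows from the text and needs no assumption.

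The size does need assumptions: separate analysis of each item, two-sided 5% between-arm rank-sum tests, 14 versus 7 completers, and the stated correlations. Under these, at least one false symptom result favouring Duobrii has a chance of about 22–33% over three visits. Near-independence would raise it to about 50%, and looking at week 12 only would lower it to about 10–17%. Even with only four outcomes, a false benefit on at least one has a chance of about 15–18% over three visits. All are well above the 2.5% for one pre-specified score. This weakens any symptom claim; it does not undermine the lesion-count analysis.

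**What to change.** - Limit the primary hypothesis to lesion counts at week 12, compared between arms. Reconcile this with Data Analysis, Primary Endpoint, where the primary test is pre/post and the between-arm test is secondary.
- Name one symptom score at week 12 as the key secondary (worst itch over seven days is one example), with its between-arm test, level and sidedness. Test it at 5% only if the between-arm lesion-count test succeeds.
- Report all other scores, visits and pre/post contrasts as estimates with intervals, without significance claims.
- Report dyspigmentation with estimates and intervals whatever the efficacy results. Potential Risks lists hypopigmentation for both products, so the outcome is partly one of safety and should not wait behind an efficacy test.

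**Cost.** Protocol and SAP wording change, but no participants, visits or data are added: Appendix A already schedules the lesion counts and the DLQI, NRS and severity scores. Fewer results can be called significant. The first step also has limited power. If it is the plan's Z-test for a 50-point difference, power with 14 versus 7 completers is about 73–87% one-sided or 60–80% two-sided, over placebo rates of 5–50%. The symptom score would go untested whenever that step fails.

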## **STUDY OBJECTIVE**

Evaluate the efficacy and safety of Duobrii in the management of early to mild AKN

## **ENDPOINTS:**

### **Primary Endpoint**

- The primary endpoint will be clinical improvement as assessed by lesion counts and captured by photography.

### **Secondary Endpoint**

- Patient reported outcome, improvement in severity of AKN associated symptoms as well as degree of dyspigmentation.

## **STUDY DESIGN OVERVIEW:**

Following IRB approval, we will conduct a single center, prospective, double-blinded placebo vs. active-control trial assessing the efficacy of the vehicle vs. Duobrii, respectively, in the management of AKN over 3 months.

Blinding will be performed by pharmacy and research staff. In addition, different investigators will do the clinical enrollment and follow up vs. statistical analysis.

Patients with class I and class II AKN (Appendix C) from our various clinics at our Skin of Color Center will be screened with plan to enroll 30 participants after obtaining written informed consent. In addition, flyer announcement of our trial will be distributed and active patient recruitment will be conducted at various local barber shops and social media platforms (instagram, twitter and facebook) to increase patient recruitment.

Enrolled participants will be instructed to apply placebo (n=10) vs. active (n=20) to affected area of the occipital scalp for 4 weeks once a day (label use). Each application will be approximately 1g. Following the 4 weeks, participants will be instructed to increase application to twice daily (BID; off-label; at least 8 hours apart) for one week. Investigators will conduct a phone visit on week 5 to discuss any potential side effects with this increased dose. If tolerated, this BID regimen will be carried throughout the length of the study. If BID is not tolerated (if irritation occurs), then Bryhali will be used as a “rescue treatment” once daily for 1 week before the subject returns to BID treatment with Duobrii. If irritation recurs, subjects will be instructed to alternate Duobrii and Bryhali (ie Duobrii BID one day, followed by Bryhali QD the next day, Duobrii BID the next, and so on). Alternating topical steroid use and stepping down topical steroid strength have been known to reduce lesion count in AKN. If irritation continues to persist, then participants will be instructed to use Bryhali QD for five days a week and Duobrii BID two days a week. If participants still experience irritation with this regimen, then subjects will be transitioned entirely to Bryhali QD for the remainder of the study. In case of clearance earlier than the end of the study, participants will be instructed to continue their respective regimen to completion of the study. Gentle hair care regimen will be recommended for duration of the length of the study; with unscented shampoo & conditioner (such as Head & shoulder) and Vaseline to scalp as moisturizer to minimize risk of contact dermatitis. In addition, patients will be instructed to postpone any form of hair coloring or chemical hair processing until after the study is over.

Participants will be followed with visits scheduled at baseline, 4 weeks, 8 weeks and 12 weeks. At each visit, participants will complete surveys regarding the severity of AKN's associated symptoms (pain, pruritus, burning etc.) as well as the dermatology quality of life index (DLQI) and numerical rating scale (NRS) surveys (Appendix B&D). In addition, photographs will also be obtained for global assessment and lesion count will be performed. The investigator will assess the treatment area for any dyspigmentation and document the % area affected within the treatment area at each visit. Tape strips will also be collected from lesional (occipital scalp) and non-lesional (frontal scalp) at Baseline and Week 12. There will be a phone call visit at week 5 to assess tolerance of medication increase and a safety follow-up visit at Week 14. Statistical analysis will be performed. Throughout the length of the study, any adverse events (AEs) related to the treatment will be recorded.

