## **SAFETY MONITORING**

The study will be conducted in accordance with our department's Standard Operating Procedures, which are based on US FDA Title 21 Code of Federal Regulations and ICH Good Clinical Practice guidelines.

An investigator will review all laboratory results and assess for adverse events. The principal investigator will be informed of all adverse events. In the event that a subject's safety is compromised, the investigator will discontinue the subject immediately.

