## **POTENTIAL RISKS**

### **Duobri:**

Participants will be advised to avoid a severe sunburn and/or prolonged periods of sunlight exposure. If a sunburn does occur, subjects will be instructed to consult with their

healthcare provider and discontinue Duobrii until sunburn is healed. Hats or other head coverings will be strongly encouraged if direct sunlight exposure is unavoidable.

The following side effects are grouped by likelihood and severity.

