### **CONTRAINDICATIONS/CAUTIONS:**

**Duobrii:** 1) Hypersensitivity to drug/class/compound 2) Pregnancy 3) Breastfeeding if applied on nipples 4) Female patients of reproductive potential 5) Pediatric patients 6) Skin infection 7) Photosensitivity 8) Sunburn 9) History of skin cancer

**Bryhali:** 1) Hypersensitivity to drug/class/compound 2) Pediatric patients 3) Skin infection

**Definition of an AE:** Any untoward medical occurrence in a subject administered a pharmaceutical product that does not necessarily have a causal relationship with the treatment. An AE can therefore be any unfavorable and unintended sign (including an abnormal laboratory finding), symptom, or disease temporally associated with the use of a medicinal (investigational) product, whether or not considered related to the investigational medicinal product.

Investigational Medicinal Product (IMP) includes the drug under evaluation and the comparator drug(s) if specified as part of the research objective, given at any time during the study. Medical conditions/diseases present before starting the drug of interest are only considered adverse events if they worsen after starting the drug of interest.

The occurrence of adverse events will be sought by non-directive questioning of the patient at each visit during the study. Adverse events also may be detected when they are volunteered by the patient during or between visits or through physical examination, laboratory test, or other assessments. All adverse events will be recorded in the study database including the following information:

1. the severity grade (mild, moderate, severe)
2. its relationship to the drug(s) of interest (suspected/not suspected)
3. its duration (start and end dates or if continuing at final exam)
4. whether it constitutes a serious adverse event (SAE)

A SAE is any untoward medical occurrence that at any dose:

- results in death
- is life-threatening
- requires inpatient hospitalization or prolongation of existing hospitalization
- results in persistent or significant disability/incapacity

- is a congenital anomaly/birth defect
- is otherwise a significant medical event

This includes any SAEs likely to arise from the trial indication or progression of underlying/concomitant illness(es) (e.g. progression of cancer in oncology trials), unless specified in the protocol as study specific exemptions.

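### The week-4 increase to off-label twice-daily use is not conditional on tolerating once-daily use, although adverse events are already sought in person at week 4

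*Combined protocol and SAP*

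**What the plan says.** The regimen is in the Study Design Overview. Participants in both arms apply about 1 g once a day for four weeks, which the protocol calls label use. Then: "Following the 4 weeks, participants will be instructed to increase application to twice daily", marked as off-label, for one week. Continuation depends on tolerance: "If tolerated, this BID regimen will be carried throughout the length of the study". The Bryhali steps open on this trigger: "If BID is not tolerated (if irritation occurs". The dosing check comes after the change: "There will be a phone call visit at week 5 to assess tolerance of medication increase".

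Week 4 is listed as an in-person visit under Discontinuation of Treatment and Withdrawal of Subjects. Contraindications/Cautions has adverse events sought at every visit and graded mild, moderate or severe. Appendix A marks adverse events and clinical assessment at week 4.

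Four other provisions bear on the point:

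- Safety Monitoring: if a subject's safety is compromised, "the investigator will discontinue the subject immediately".
- Discontinuation of Treatment and Withdrawal of Subjects: a confirmed, suspected-related event of grade 3 or higher is one possible reason for withdrawal, in a list that is expressly not exhaustive.
- Potential Risks: after a sunburn, the participant is to "discontinue Duobrii until sunburn is healed".
- Contraindications/Cautions: "Adverse events also may be detected when they are volunteered by the patient during or between visits".

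**The concern.** The step from label to off-label frequency is the riskiest dosing change in the trial, and Potential Risks lists irritation, burning and pruritus among the common reactions to Duobrii. The protocol sets out several steps for irritation that appears on twice-daily use. It gives none for irritation already present on once-daily use when the increase falls due.

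The information needed for that decision is collected face to face at week 4, but nothing in the text uses it. An investigator who follows the wording tells a participant with ongoing mild or moderate irritation to double the product. One who holds the dose departs from the written regimen, and different investigators may do so on different grounds. What is at stake is avoidable discomfort and consistent conduct.

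**Working it through.** **Does any existing rule cover irritation on once-daily use at week 4?**

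| Provision | What it does | Holds the increase for mild or moderate irritation? |
|---|---|---|
| Tolerance condition (Study Design Overview) | Governs continuing twice-daily use | No, applies after the increase |
| Bryhali steps (Study Design Overview) | Triggered by intolerance of twice-daily use | No, applies after the increase |
| Safety Monitoring | Discontinues the subject if safety is compromised | No, it ends participation |
| Discontinuation and Withdrawal | Possible withdrawal, including for a related event of grade 3 or higher | No, not a hold |
| Sunburn advice (Potential Risks) | Temporary stop until healed | No, sunburn only |
| Events volunteered between visits (Contraindications/Cautions) | Can bring rescue forward | No, shortens exposure after the increase |

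The gap is therefore real. The sunburn advice shows that the protocol accepts temporary stops in principle.

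**How much extra product is involved before the week-5 call?** The plan gives no figure to reproduce. The inputs are about 1 g per application, 7 applications a week once daily and 14 a week twice daily (Study Design Overview).

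- A participant who stays on twice-daily use until the call has 14 − 7 = 7 extra applications, about 7 g.
- A participant who reports irritation on day *d* and starts Bryhali the next day has used 2*d* applications that week. A participant held on once-daily use for the whole week uses 7. The amount avoided by holding is 2*d* − 7:

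| Day reported | 1 | 2 | 3 | 4 | 5 | 6 | 7 |
|---|---|---|---|---|---|---|---|
| Applications, current text | 2 | 4 | 6 | 8 | 10 | 12 | 14 |
| Avoided by a one-week hold | −5 | −3 | −1 | 1 | 3 | 5 | 7 |

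The saving of 7 is thus the maximum. For someone who reports in the first three days there is none, because rescue would already have replaced Duobrii.

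**What does a hold cost in exposure?** Without a hold, 12 weeks give 28 + 8 × 14 = 140 applications. A one-week hold followed by twice-daily use gives 28 + 7 + 7 × 14 = 133. The loss is 7/140 = 5%. Each further week held costs another 5%, up to 8 × 7 = 56 applications (56/140 = 40%) if the participant never increases.

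**Is there a saving over the rest of the trial?** None can be claimed. A participant held on once-daily use through week 12 uses 8 × 7 = 56 Duobrii applications after week 4. Under the current text, a participant who stays on twice-daily use until the call and then works down the rescue steps uses:

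- 14+0+14+7+4+0+0+0 = 39, with one week per step;
- 14+0+14+7+7+4+4+0 = 50, with two weeks each on the alternating-day and two-day steps;
- 14+0+14+5×7 = 63, settling on alternating days.

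Apart from the one-week first rescue, these step durations are assumptions, and 56 falls inside their range.

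**The case against.** The best case against is that the existing text already limits the harm. Week 4 is a face-to-face visit, the discontinuation reasons are open-ended, and a participant already irritated at week 4 could meet the rescue trigger on the first day of twice-daily use and report it then. What remains is a clinical judgement about mild or moderate irritation, worth at most about 7 g over one week, in an unknown number of people. All of that stands, and it sets the size of the point. It does not supply the missing condition: the instruction is still to increase, and each of these protections either ends participation or acts after the increase.

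A second objection is that a remedy can be worse than the gap. Sending participants with unresolved once-daily irritation into the existing Bryhali steps would, after one week, put them on the twice-daily regimen they were being spared. It would also give an active steroid to placebo participants on a new trigger, while Investigational Drug Supply requests Bryhali for only 20 subjects, the size of the Duobrii arm. This also stands, and it is why the fix below leaves those steps alone.

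A reader might infer more than the documents support. They do not say that rescue must wait for the week-5 call, since events can be volunteered at any time. Nor do they leave participants without protection at week 4, since severe events, compromised safety and sunburn are covered.

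**Conclusion.** The point holds as a minor safety matter. The increase to off-label twice-daily use is instructed whatever a participant's tolerance of once-daily use, and the findings of the week-4 visit have no written bearing on it. The avoidable exposure is at most about 7 applications (7 g) before the week-5 call, and less or none for a participant who reports early.

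This rests on the regimen being followed as written, on about 1 g per application, and on rescue starting the day after irritation is reported. The documents give no rate of irritation on once-daily use, so the number affected cannot be estimated.

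It might be tempting to read this as a threat to power, retention or the lesion-count analysis. Nothing in the documents links the missing condition to any of these, and no such effect is claimed.

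**What to change.** Reword the regimen in the Study Design Overview along these lines:

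*At the week-4 visit, participants who are tolerating once-daily application will increase to twice daily. Participants with application-site irritation that the blinded investigator judges treatment-related, and that is new or worsened since baseline, stay on once-daily assigned product. They are re-checked at the week-5 call, or sooner if it worsens, and increase only once it has resolved, with a tolerance call one week later.*

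Apply the rule identically in both arms. Do not require twice-daily use of anyone who has not tolerated once-daily use. Leave the Bryhali steps as they are, for intolerance of twice-daily use. The threshold needs both relatedness and change from baseline because the trial also surveys "associated symptoms (pain, pruritus, burning etc" as features of the disease, and those alone should not trigger a hold.

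The cost is a few lines of text, a footnote in Appendix A, an IRB amendment, and one extra call for each held participant who later increases. Product use for a one-week hold falls from 140 g to 133 g, within the 200 g of Duobrii and 180 g of vehicle per subject under Investigational Drug Supply. The downside is lower exposure for held participants: 5% for one week, more if irritation persists. A held participant also has no Bryhali step while held, so worsening would be handled by the earlier re-check and the existing discontinuation provisions.
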